#### **5.1.3 Usual Care First Group**

1. Following completion of the initial mini-BAL, patients in the Usual Care First group will continue to receive mechanical ventilation according to the University of Michigan ARDS protocol High-PEEP arm (Appendix C). Confirmation will be made to assure compliance with the High-PEEP table.
2. Approximately six hours after randomization a second mini-BAL will be performed (5.1.2 above).
3. Following completion of the second mini-BAL procedure Usual Care First patients will crossover and receive PEEP titration by EIT (see 5.1.5 below) for an additional 14-18 hours at which time a third mini-BAL will be performed. The protocol will end after the third mini-BAL has been performed and the patient will return to mechanical ventilation PEEP titration via the University of Michigan ARDS protocol high PEEP arm. All ventilator management will return to the clinical team.

#### **5.1.4 Electrical Impedance Tomography (EIT) First Group**

1. Following completion of the initial mini-BAL, patients in the EIT first group will have best PEEP determined by EIT (see 5.1.5 below).
2. Approximately six hours after randomization a second mini-BAL will be performed (5.1.2 above).
3. Between initial PEEP setting and the 2nd mini-BAL, ventilator management will follow the University of Michigan ARDS protocol, with the exception that PEEP will be left at the EIT determined level and only FiO2 adjusted for oxygenation issues. If FiO2 reaches 1.0, the clinical team will use their discretion to manage PEEP.
4. Following completion of the second mini-BAL procedure EIT first patients will crossover and receive PEEP titration by the University of Michigan ARDS treatment protocol using the high PEEP table for an additional 14-18 hours at which time a third mini-BAL will be performed. The protocol will end after the third mini-BAL has been performed and the patient will continue to be receive mechanical ventilation PEEP titration via the University of Michigan ARDS protocol high PEEP arm. All ventilator management will return to the clinical team.

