### **5.1. Study Initiation**

At the time of randomization all study subjects will be receiving the standard University of Michigan ARDS protocol high PEEP arm (Appendix B). All patients will receive lung protective ventilation (LPV), attempting to achieve a plateau pressure (Pplat)  $\leq$  30 cm H2O with tidal volume by ideal body weight being allowed as high as 8 cc/kg and as low as 4 cc/kg in so doing.

Following randomization patients will undergo a mini-BAL according the methodology undertaken by Ranieri and colleagues [16] prior to institution of the protocol arm.

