## 6.3 Assessments During Study

The following data will provide the basis for assessing protocol compliance and safety as well as between-group differences in several efficacy variables. Data for each of the variables will be recorded at the times shown in the Time-Events schedule (Appendix F).

It is expected that setting PEEP using EIT will take between 20-40 minutes and 5-10 minutes using the High-PEEP table. To standardize the time from new PEEP exposure until inflammatory mediators are obtained, time 0 is defined as the time at which the PEEP setting is finally established. Hour 6 is subsequently six hours after PEEP is initially established and the time of the 2nd mini-BAL. Time 0 resets at the point of crossover, as the time at which the new PEEP level is established. (see Appendix F)

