## F. Time-Event Schedule

Clock example	Study hour	Procedures	Vent data	EIT data	HR/ BP	SpO2	ABG	Cytokines	Comments
closest	BL, pre	BL Assess	X		X	X	X		
8:00		BAL#1			X	X		X	BAL procedure time ~30 min
8:30	0	Set PEEP #1	X	X	X	X			Set EIT ~20-40 min vs table ~5-10 min
9:30	1						X	X	ABG 1 H after setting PEEP
10:30	2								
11:30	3								
12:30	4								
13:30	5								
	pre BAL	Assessment	X	X	X	X	X		
14:30	6	BAL #2			X	X		X	BAL procedure time ~30 min
15:00	0	Set PEEP #2	X	X	X	X			
16:00	1					X	X		ABG 1 H after setting PEEP
17:00	2								
18:00	3								
19:00	4								
20:00	5								
21:00	6								
22:00	7								
23:00	8								
0:00	9								
1:00	10								
2:00	11								
3:00	12								
4:00	13								
5:00	14								BAL #3, anytime between hr 14-18
6:00	15								
7:00	16								
8:00	17								
9:00	pre-BAL	Assessment	X	X	X	X	X		
9:00	18	BAL #3			X	X		X	BAL procedure time ~30 min

Data Collected:	Ventilator: mode, set VT, RRset, RRtot, VE, FiO2, PEEP, Ppeak, Pplat, Pmean, PEEPtot,
	vent calcs: drive-P, Cst, Cdyn,
	EIT: delta-EELI, ODCL; COV, GI Index, Regional compliance
	ABG: pH, PaCO2, PaO2, SaO2, BE, HCO3 (if collected for standard of care)
	Cytokines: per protocol

**Definition of Time:** Time 0 is when PEEP is established

Time 6 is 6 hours after PEEP is set

Reset time frames at cross-over

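### The arm instructions time the second mini-BAL and crossover from randomization, while 6.3 and Appendix F time them from established PEEP; followed literally, they give EIT-first patients about 290-310 minutes on EIT PEEP, not 360

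*Combined protocol and SAP*

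**What the plan says.** Two clocks for the same event stand in the current text.

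- **From randomization.** Section 5.1.4(2), for the EIT-first group, reads: "Approximately six hours after randomization a second mini-BAL will be performed". Section 5.1.3(2) has the same sentence for Usual Care First. In both sections crossover follows completion of that lavage.
- **From established PEEP.** Section 6.3 gives its purpose, "To standardize the time from new PEEP exposure until inflammatory mediators are obtained", and its rule: "time 0 is defined as the time at which the PEEP setting is finally established". It continues "Hour 6 is subsequently six hours after PEEP is initially established and the time of the" second mini-BAL. Appendix F agrees: "Time 6 is 6 hours after PEEP is set". Section 1.1 also counts six hours from EIT recruitment or from table-guided PEEP.

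The order of events and their durations are given too. Section 5.1 states "Following randomization patients will undergo a mini-BAL", before the assigned arm begins. Appendix F gives "BAL procedure time ~30 min". Section 6.3 gives the setting times: "It is expected that setting PEEP using EIT will take between 20-40 minutes and 5-10 minutes using the High-PEEP table".

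Section 5.1 adds that every patient is already on the institution's high-PEEP arm at randomization, and 5.1.3(1) has Usual Care First patients continue on it.

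**The concern.** Hour 6 is the post-baseline, pre-crossover comparison between groups that section 7 names. Ventilator and EIT data are collected immediately before the hour 6 lavage, so the timing governs physiologic endpoints as well as biomarkers. Because crossover follows that lavage, the starting event also fixes the length of the first treatment period.

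A coordinator working from the arm-specific steps would count from randomization. The first lavage and the EIT titration would then use up part of the six hours, by an amount that varies from patient to patient. Section 6.3 was written to prevent exactly this. A coordinator working from 6.3 would sample later and would appear to deviate from 5.1.3 or 5.1.4.

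**Working it through.** **Inputs.** Second lavage at 360 min (5.1.3, 5.1.4, 6.3, Appendix F). First lavage about 30 min (Appendix F). PEEP setting 20-40 min by EIT and 5-10 min by table (6.3). Delay from randomization to the first lavage is not stated; it is taken as 0 min, which gives the longest exposure.

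**The plan's own figure.** Appendix F's clock example has hour 0 at 8:30 and the second lavage at 14:30: 14:30 - 8:30 = 360 min. This reproduces the six hours. The example is loose, however. It starts the first lavage at 8:00, so that lavage ends at 8:30 and no time is left for setting PEEP. If setting began at 8:30, a 14:30 lavage would come 360 - 40 = 320 to 360 - 20 = 340 min after EIT PEEP is established, or 360 - 10 = 350 to 360 - 5 = 355 min after table PEEP.

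**Randomization clock.** Time from established PEEP to second lavage = 360 - delay - 30 - setting time.

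| Group | Calculation (delay 0) | Result | Short of 360 min |
|---|---|---|---|
| EIT-first | 360 - 30 - 40 to 360 - 30 - 20 | 290-310 min | 50-70 min (13.9-19.4%) |
| Usual Care First, 6.3 time 0 | 360 - 30 - 10 to 360 - 30 - 5 | 320-325 min | 35-40 min (9.7-11.1%) |

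**What the second row means.** It measures time from the 6.3 time 0 only. These patients are on the high-PEEP arm before randomization and stay on it, so at randomization + 360 min they have had at least 360 min of table-guided PEEP. The loss of exposure to a new PEEP setting falls on EIT-first.

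**Sensitivity, EIT-first.**

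- A 30 min delay before the first lavage gives 260-280 min; 60 min gives 230-250 min.
- The setting time may run longer than 40 min. Section 5.1.5 lowers PEEP from 20 by 2 cm H2O every 5-10 min. Five reductions, to 10, take 5 x 5 = 25 to 5 x 10 = 50 min, before counting electrode stabilization and recruitment. At 50 min, exposure is 360 - 30 - 50 = 280 min.

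**Established-PEEP clock.** Both groups have 360 min after time 0. The second lavage falls at 30 + setting + 360 after randomization: 410-430 min (EIT-first) or 395-400 min (Usual Care First). That is 35-70 min later than the arm instructions put it.

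**Third lavage.** Each patient has one setting by each method, 25-50 min in total. On the established-PEEP clock the third lavage starts 30 + 360 + 30 + (25 to 50) = 445-470 min after randomization, plus 14 to 18 h:

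- hour 14: 1285-1310 min = 21.4-21.8 h
- hour 16: 1405-1430 min = 23.4-23.8 h
- hour 18: 1525-1550 min = 25.4-25.8 h

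On the randomization clock only the second setting (5-40 min) is added. Hour 18 is then 360 + 30 + (5 to 40) + 1080 = 1475-1510 min = 24.6-25.2 h. Appendix F's example, from 8:00 to 9:00 the next day, runs 25 h.

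**The case against.** The best defense is that the intended clock is already clear. Section 6.3 sends data timing to Appendix F, which lists the second lavage at study hour 6 and defines that hour from established PEEP, and section 1.1 agrees. On this view 5.1.3(2) and 5.1.4(2) carry a leftover phrase, softened by the word approximately. The first part stands: a careful reader would conclude that 6.3 governs. But no readable text says it overrides the arm steps (the Appendix B flowchart is not shown and cannot be checked). An approximate target also allows scatter around one starting event; it does not reconcile two starting events, and here the shortfall always runs the same way.

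A reader might infer that both arms are under-exposed, or that the arithmetic gap between them, 320 - 310 = 10 to 325 - 290 = 35 min, is a true imbalance in exposure. The documents do not support that, because the Usual Care First figure counts from a defined time 0 while the treatment itself started earlier.

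A reader might also infer that the hour 6 comparison is biased by a known amount. Nothing in the documents links 50-70 min of exposure to a change in any endpoint, and the same plan accepts a four-hour window for the third lavage. Nor is hour 6 the only between-group information before crossover: 6.3 also lists hour 0 ventilator and EIT data, and hour 1 blood gases where available, neither of which runs on the randomization clock.

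**Conclusion.** The conflict is real and sits in the operative steps for each arm. Followed as written, those steps shorten the EIT-first period on the new PEEP to about 290-310 min, 14-19% below the intended six hours, and bring sampling and crossover forward together. This rests on three things: the first lavage starting at randomization, a lavage of about 30 min, and the protocol's 20-40 min setting time taken at face value. A delay before the first lavage, or a longer decremental trial, lowers the figure.

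If staff already follow 6.3, there is no shortfall and only the wording needs correcting. The point should be corrected because the remedy is cheap and protects an interval the protocol set out to standardize. It does not show that any result would be distorted.

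**What to change.** 1. In 5.1.3(2) and 5.1.4(2), time the second mini-BAL six hours after PEEP is established by the assigned method (time 0, section 6.3) in place of randomization. Keep crossover immediately after that lavage.
2. In sections 3 and 11, let the protocol and the adverse-event period run through completion of the third mini-BAL in place of a fixed 24 hours.

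The second change is needed because section 11 ends adverse-event ascertainment 24 hours after enrollment. Taking enrollment as randomization, the third lavage passes 24 h from about hour 16.8-17.4 on the present wording (1440 - 430 = 1010 to 1440 - 395 = 1045 min). With the first change alone it would do so from about hour 16.2-16.6 (1440 - 470 = 970 to 1440 - 445 = 995 min), leaving more of the 14-18 h window uncovered.

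The cost is a few replaced phrases, with no new procedure or data field. The second lavage falls 35-70 min later, and the third starts about 21.4-25.8 h after randomization, so some patients are followed for adverse events beyond 24 h. The change fixes time since established PEEP at 360 min in both arms; it does not remove the Usual Care First group's earlier time on the high-PEEP table, which comes from the design.

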### 5.1.5 EIT PEEP Titration

Electrical impedance tomography (EIT) is a non-invasive, non-radioactive, bedside imaging tool. EIT entails the use of a belt like apparatus which is placed circumferentially around a patient's chest. A small, imperceptible current is applied and regional voltages are subsequently measured to determine ventilation related impedance changes across the thoracic cross section created by the belt. Reconstruction algorithms are then utilized to generate real time tomographic images on a breath by breath basis. The Drager Pulmovista 500, which is commercially available in Europe and Canada will be used for the generation of EIT images (Appendix D).

In a review of the recent EIT literature, we found 7 studies [18-22] using the Drager EIT device in adults to either provide feedback on the effects of PEEP or to determine a specific level to set PEEP (see Appendix E). All 7 studies are observational in design, ranging in sample size from 10 to 39 patients. Five were studies of patients with ARDS. The methods used in most of these studies provided a breathing pattern at a modest pressure level (recruitment maneuver) to open the maximum number of lung units for that pressure and then gradually reduced the end-expiratory pressure (decremental PEEP) to observe the patterns of variation in ventilation.

The most common EIT variables used to assess PEEP include:

1. Regional compliance: it is analogous to dynamic compliance, but rather than using a change in tidal volume in the numerator, it uses the tidal impedance variation (TIV). Also, dynamic and static compliance are global measurements, while EIT regional compliance reflects the compliance in each of the four regions of interest (generally dorsal, medial-dorsal, medial-ventral and ventral)
2. EELI (end-expiratory lung impedance): it is analogous to the end-expiratory lung volume or functional residual capacity (FRC)
3. ODCL (overdistension-collapse): this index estimates the percentage and location of lung overdistension and atelectasis (collapse) during a decremental PEEP trial
4. GI (global inhomogeneity) index: this quantifies the ventilation distribution in the lungs and provides information on the degree of homogeneity of lung ventilation
5. COV (center of ventilation): it reflects the distribution of regional ventilation in a dependent-to-non-dependent direction

#### Patient preparation:

1. The patient should be sedated adequately to suppress respiratory effort.
2. The EIT belt will be placed at the level of the 5th intercostal space. A period of 5-10 minutes will be allowed for electrode stabilization and calibration.

#### PEEP Titration Procedure:

1. The procedure involves two phases: a recruitment phase followed by a gradual reduction in the end-expiratory pressure phase (Decremental PEEP).

2. Recruitment Phase: Pressure control with a drive pressure of 15 cm H2O and PEEP of 20 cm H2O (ie, 35/20) will be applied for 5-10 breaths and then increased to a PEEP of 25 cm H2O (ie, 40/25) for 1 minute.
3. Decremental PEEP: In volume control, VT will be set to 6 mL/kg PBW and PEEP to 20. Every 5-10 minutes, PEEP will be reduced by 2 cm H2O. PEEP will be reduced until one of the following occurs: 1) drop in EELI in any region during the stabilization period by >10%, 2) PEEP = 5 cm H2O, or 3) patient develops hemodynamic instability or SpO2 <88%.
4. The best EIT-PEEP is identified as that which demonstrates the best compromise in over-distension (OD) and collapse (CL), as determined by the ODCL EIT variable.

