## GENERAL COMMENT

Low VT and minimizing Pplat is the only ventilation strategy with a high level of evidence of mortality benefit in ARDS. Therefore, a lung protective ventilation strategy (LPVS) following the ARDS Network strategy (using pressure or volume ventilation) to limit VT (target 6 mL/kg; reduce to 5 or 4 for high Pplat, 7 or 8 for double-triggering) and Pplat ( $\leq$ 30 cm H2O) should be the initial and primary strategy for all ARDS patients.

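### Step 3 of the EIT titration puts every patient on 6 mL/kg at PEEP 20, including those whose tidal volume was already cut to 4-5 mL/kg for high plateau pressure

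*Combined protocol and SAP*

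**What the plan says.** All patients enter on the site's high-PEEP strategy: "At the time of randomization all study subjects will be receiving the standard University of Michigan ARDS protocol high PEEP arm". Section 5.1 sets a Pplat aim of 30 cm H2O or less, "with tidal volume by ideal body weight being allowed as high as 8 cc/kg and as low as 4 cc/kg in so doing". The General Comment in Appendix C gives the working rule: "target 6 mL/kg; reduce to 5 or 4 for high Pplat, 7 or 8 for double-triggering".

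The EIT titration has its own settings. After a short recruitment phase, step 3 reads: "In volume control, VT will be set to 6 mL/kg PBW and PEEP to 20". PEEP then falls by 2 cm H2O every 5-10 minutes; "PEEP will be reduced until one of the following occurs": a regional end-expiratory impedance loss of more than 10%, PEEP 5, or instability or saturation below 88%. Step 4 picks the PEEP with the best balance of over-distension and collapse.

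Both sequences pass through step 3. The EIT First group does so at the start. For the other group Section 5.1.3 says: "Usual Care First patients will crossover and receive PEEP titration by EIT (see 5.1.5 below) for an additional 14-18 hours".

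**The concern.** The patients on 4-5 mL/kg are those in whom the site protocol has already judged Pplat too high at 6 mL/kg. Step 3 returns them to 6 mL/kg and, for most of the PEEP table, does so at or above the PEEP they were on. Two instructions in the same protocol then conflict, and staff following the more specific one will raise VT.

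The exposure belongs only to the EIT titration and comes before time 0 as Section 6.3 defines it. The trial's hypothesis is that EIT titration causes less lung inflammation, and Section 9.5 expects it to be, if anything, safer than the table. A setting that suspends lung protection in the stiffest lungs fits poorly with both.

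**Working it through.** The plan gives no figure on this point, so there is none to reproduce. The check is pressure arithmetic.

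**Inputs**
- Titration VT 6 mL/kg, starting PEEP 20, steps of 2 cm H2O, 5-10 minutes per level (Section 5.1.5, step 3).
- Pplat aim of 30 or less, VT 4-8 mL/kg (Section 5.1); reduction to 5 or 4 for high Pplat (Appendix C).
- Table PEEP T from the Higher PEEP table in Appendix C: at most 20 at steps 1-12, and 22-24 at steps 13-17.
- Assumptions: VT was cut because Pplat at 6 mL/kg exceeded 30 at the current T, and static compliance (Cst) is unchanged.

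**Bound.** Pplat = PEEP + driving pressure. Write DP6 for the driving pressure at 6 mL/kg.
1. VT was cut because T + DP6 > 30, so DP6 > 30 - T.
2. At PEEP 20 and 6 mL/kg, Pplat = 20 + DP6 > 50 - T.
3. Pplat stays above 30 at every level from 20 down to T. For even T that is (20 - T)/2 + 1 levels, unless an end event comes first.
4. To bring Pplat at PEEP 20 to 30, DP6 must fall to 10, so Cst must rise by more than (30 - T)/10 - 1.

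| Table PEEP T | Table steps | DP6 above | Pplat at PEEP 20 above | Levels above 30 | Time (min) | Cst gain needed, more than |
|---|---|---|---|---|---|---|
| 20 | 10-12 | 10 | 30 | 1 | 5-10 | 0% |
| 18 | 9 | 12 | 32 | 2 | 10-20 | 20% |
| 16 | 7-8 | 14 | 34 | 3 | 15-30 | 40% |
| 14 | 6 | 16 | 36 | 4 | 20-40 | 60% |

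These are minima. Take a patient held at exactly Pplat 30 at PEEP 16:
- On 4 mL/kg, driving pressure is 14, so DP6 = 14 x 6/4 = 21. Pplat at PEEP 20 is 41, and it stays above 30 at six levels (PEEP 20 to 10), or 30-60 minutes.
- On 5 mL/kg, DP6 = 14 x 6/5 = 16.8. Pplat at PEEP 20 is 36.8, and it stays above 30 at four levels, or 20-40 minutes.

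**Where the bound stops.** At T = 22 it gives only Pplat > 28 at PEEP 20, and at T = 24 only > 26, so an excess over 30 no longer follows.

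**With the reduced VT kept.** If Pplat was 30 or less at T on the lower VT, then at PEEP 20 it is at most 20 + (30 - T) = 50 - T. So 50 - T is the dividing line: step 3 as written lies above it, and the retained VT lies at or below it. At T = 16, with DP6 at its bound of 14, 5 mL/kg gives 20 + 14 x 5/6 = 31.7 and 4 mL/kg gives 20 + 14 x 4/6 = 29.3. The patient above who sat at Pplat 30 on 4 mL/kg would reach 34 instead of 41. Keeping the VT helps, but it secures 30 or less only when T is 20 or higher.

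**The case against.** Much of the opposing case stands as a limit on severity. The Pplat value is an aim, not a ceiling. Step 2 deliberately applies 40/25 for one minute, so some high pressure is intended, and recruitment may raise compliance enough to soften the bound. A single titration VT is also a recognisable choice: Appendix E lists volume-control titrations at 7 mL/kg in ARDS and 10 mL/kg in perioperative patients. The one listed study that allows 5 or 4 mL/kg for Pplat does so at baseline, not expressly in its decrement. The Appendix B figure and the on-file Appendix I policy could not be read, and either might hold a pressure limit. None of this shows that raising VT in already-reduced patients was meant, and step 3 lasts 5-10 minutes per level against step 2's single minute.

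Three stronger readings are tempting, and the documents do not support them.
- *The list of end events lacks a Pplat stop rule.* Those events end the downward PEEP steps. At fixed VT and stable compliance, Pplat is highest at the first level and falls with each step, so a Pplat stop there would hold PEEP high.
- *PEEP is chosen at a larger VT than is delivered, which biases the EIT arm.* In the EIT First group the site protocol resumes "with the exception that PEEP will be left at the EIT determined level", so VT can fall again. It needs to only if EIT PEEP + DP6 exceeds 30. At the mean EIT PEEP of 11.3 in one Appendix E cohort, DP6 of 12, 15 or 18 (assumed) gives 23.3, 26.3 or 29.3, and VT can stay at 6. Where a mismatch remains, its direction and size depend on a lung model that the documents do not supply.
- *Every EIT titration exceeds Pplat 30.* Patients on an unreduced 6 mL/kg fall outside the argument, as do those on table PEEP 22-24, for whom step 3 starts 2-4 cm H2O below table PEEP.

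The management of PEEP after crossover to EIT in Section 5.1.3 is a separate matter.

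**Conclusion.** The point holds in a limited form. As written, step 3 overrides the plan's own VT reduction for patients cut to 4-5 mL/kg for high Pplat. For those on table PEEP of 20 or less, Pplat at the first level exceeds 50 - T: above 30, 32, 34 and 36 at T = 20, 18, 16 and 14, for at least one to four levels of 5-10 minutes if no end event intervenes. This rests on unchanged compliance and on VT having been cut because Pplat exceeded 30 at that PEEP. How many of the 20 patients are affected cannot be derived and could be none, so no effect on the biomarker comparison can be claimed. Severity is minor; this is a cheap improvement.

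**What to change.** Reword the VT setting in step 3 along these lines: *set VT at 6 mL/kg PBW, or at the lower value already in use where it was reduced for Pplat, and hold it constant at every PEEP step.* Record the titration VT beside the tidal volume already collected at Hour 0.

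No matching upward exception is needed for patients on 7-8 mL/kg. Appendix C allows that for double-triggering, and the preparation step removes the reason: "The patient should be sedated adequately to suppress respiratory effort".

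If the investigators also want a Pplat rule, it should act before the decrement by lowering VT (to no less than 4 mL/kg) or the starting PEEP. It should not stop the decrement.

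The cost is one clause and one recorded value, with no added procedure. There are two downsides. Titration VT would differ between patients, although it stays constant within each patient, where the PEEP levels are compared. And if the chosen PEEP lets VT return to 6 mL/kg, PEEP will have been titrated at a smaller VT than the one delivered; the recorded titration VT would show this.
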